Screen potential participants by inclusion and exclusion criteria; obtain informed consent; conduct baseline survey and clinical exam: **Caries** (tooth surface level data collected by calibrated clinical examiners), **Social Cognitive variables** regarding child's oral health (motivation, self-efficacy, outcome expectations), **Moderators** from Fisher-Owens model (insurance, demographics, family size, perceived stress, physical safety/family issues, previous caries experience, parent oral health status, parent depressed mood, history of dental care, perception of dental visits, fluoride varnish, child oral health quality of life), **Parent/child oral health behaviors** (bottle/sippy cup use, diet, sugar sweetened beverages; tooth monitoring, fluoridated water/toothpaste; frequency/duration/timing of brushing or cleaning child's mouth, preventive dental visits), **parent oral health knowledge and attitudes**.

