Fluoridated water/toothpaste. This measure will be assessed at baseline, 4, 12, and 24 months after baseline. We will use items from the BRFQ (Albino et al., 2017).

Preventive dental visits. This measure will be assessed at all measurement points, and monthly during the TM program. We will use items from the BRFQ (Albino et al., 2017).

Parental knowledge, attitudes and behavior regarding oral health:

Parent oral health knowledge: 21 items. This measure assesses parental knowledge related to oral health hygiene routines and feeding practices. The overall knowledge score represents the percentage of oral health knowledge items answered correctly. We will use items from the BRFQ (Albino et al., 2017). This measure will be assessed at baseline, 4, 12, and 24 months after baseline.

Parent's attitude toward their own and their child's oral health. We will use items from the BRFQ (Albino et al., 2017). This measure will be assessed at baseline, 4, 12, and 24 months after baseline.

Parent oral health behaviors. 12 items related to parental oral health behaviors, such as oral hygiene routines.

Moderators from Fisher-Owens model:

Demographics: Insurance coverage, income, education, ethnicity, and family size. This measure will be assessed at baseline. We will assess changes in mutable variables such as income and insurance at other measurement points. We will use items from the BRFQ (Albino et al., 2017).

Perceived stress (Herrero & Meneses, 2006): We will use the 4-item version of the perceived stress scale (PSS). The PSS assesses the degree to which subjects perceive their environment and their experiences as stressful. The scale correlates well with scores on life-event measures, and has demonstrated adequate reliability (Cohen et al., 1983). This measure will be assessed at baseline, 4, 12, and 24 months after baseline.

Physical safety/family issues (Romano et al., 1991): We will use the hassles scale which has been developed and validated on low income and ethnically diverse samples. The scale assesses neighborhood safety and family issues. This measure will be assessed at baseline, 4, 12, and 24 months after baseline.

Previous caries experience: This measure will be assessed at baseline, 12 and 24-months via clinical exam utilizing a modified ICDAS

Medical history: This will be assessed at baseline, 12 and 24 months by the clinical examiner.

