4 STUDY DESIGN

This is a 2-arm, randomized controlled Phase III, single-center longitudinal trial. 850 parents or caregivers of children (< 7 years old) and their children with pediatric appointments at four targeted urban clinics will be recruited, consented, and subsequently randomized to OHT or CWT. We hypothesize that those randomized to the OHT group will have reduced incidence of caries as assessed by objective clinical exam 24- months after a baseline exam. Randomization will be a permuted block design, stratified by study site (Codman Square, Dorchester House, BMC, South End Community Health Center), and history of caries (no history of caries, any caries). Because of the sparsity of Spanish speaking participants, with Spanish speakers primarily concentrated at one site, we will not stratify by site language (English, Spanish) but only on caries history to yield 8 strata. CWT and OHT intervention arms will be matched on TM dose, duration and frequency, and employ identical features and engagement strategies for strong internal validity. External validity will be supported by the fact that participants will be proactively recruited from an existing channel (pediatric clinic appointments) and use of the text message program in their everyday lives. Recruitment sites are located in urban, low-income areas, and the population is ethnically diverse and on public assistance.

The approximate time to complete study enrollment is 1- year and the expected duration of subject participation is 2- years. A clinical exam to assess caries will take place at baseline and 12 and 24- months later. Clinical examiners are study staff and will be calibrated and blinded. Self-report surveys will take place at these time points, plus 2 and 4- months after baseline. These data will be captured through electronic data entry, in person, over the phone, or through an on-line link. Weekly and monthly assessments will also occur during the 4- month TM program (from baseline through 4-months post-baseline). The coordinating center (CC) will be University of California at San Francisco.

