5.4 Treatment Assignment Procedures

5.4.1. Randomization Procedures

In order to randomly assign participants to treatment groups at baseline, we will be using a permuted randomized block design (random sized blocks of 2 or 4 participants), stratified by study site (Codman Square, Dorchester, BMC, South End Community Health Center), and history of caries (no history of caries, any caries). Because of the sparsity of Spanish speaking participants, with Spanish speakers primarily concentrated at one site, we will not stratify by site language (English, Spanish) but only on caries history to yield 8 strata. The randomization list will be created using REDCap. Participants will be randomized by the web-based REDCap randomization module. Once the baseline questionnaire and oral assessment are completed, REDCap will automatically randomize participants into OHT or CWT, and this code as well as the TM personalization options from the baseline questionnaire will be transferred via secure API to the AH system so the first TM (OHT or. CWT) will occur within 24 hours after randomization. The automation of randomization will ensure that the RAs who have contact with participants are blind to treatment condition. The clinical examiners who will be collecting the primary outcome data will also be blinded. A detailed plan for maintenance of randomization codes, including the timing and procedures for planned and unplanned breaking of randomization codes is described in the MOP.

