12.4 Final Analysis Plan

Overview of Analytic Plan: Primary analyses will focus on the comparison of those assigned to OHT vs. CWT on oral health and behavior outcomes using all available data (i.e., restricted to those followed) and, following the intent-to-treat principle, randomized subjects will be included in the analysis regardless of their compliance with the study protocol and engagement in the study interventions. While no differences between study arms are anticipated due to randomization, preliminary analyses will explore differences between arms and variables found to differ between groups (at the $p<0.10$ level) will be adjusted for in analysis. For dichotomous outcome variables (e.g., incidence of any new caries at 24 months; use of fluoride toothpaste) analyses will use logistic regression models, with intervention effects reported as odds ratios

with 95% confidence intervals. Count data (e.g., number of new caries at 24 months) will be analyzed through Poisson regression models, if the distributional assumptions of the Poisson model are met, or negative binomial or zero-inflated models if the outcome distribution better meets the assumptions of these models. Results will be reported as rate ratios with 95% confidence intervals. Continuous variables (e.g., number of tooth brushings per week) will be analyzed through mixed effects linear regression models. Data will also be analyzed by race and gender as specified in the Notice of Grant Award, although these analyses will be exploratory due to lack of power. If follow-up falls below the anticipated 70%, primary analyses will account for missing data through inverse probability weighting using propensity scores for missingness. If follow-up meets the anticipated 70%, inverse probability weighting may be used in sensitivity analyses addressing the impact of missing data.

The two-tailed alpha 0.05 level will be used to indicate statistical significance.

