Primary aim 1: We will use logistic regression to compare the incidence of new caries in primary dentition (dmfs) over 24 months (no vs. any new caries) in OHT vs. CWT children, controlling for age, previous caries, and other relevant variables. Secondary analyses will also use logistic regression to compare OHT vs. CWT on the incidence of new caries in permanent dentition (DMFS) and mixed dentition (dmfs+DMFS). Secondary analyses of the number of new caries will be conducted using Poisson regression or related methods. Distributional assumptions of Poisson regression will be checked, and negative binomial regression models (for over-dispersion) and zero-inflated (negative binomial and Poisson) models (for excess zeros) will be considered if appropriate. Given that we are performing oral assessments at three time points (baseline, 12 and 24 months), we can also perform a tooth-level analysis of new caries in primary and permanent dentition, using mixed effects logistic regression models (Gibbons et al., 2010) to account for the multiple observations (teeth) per child.

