
Aims 2 and 3. We will compare changes in these behaviors over time in OHT vs. CWT using mixed effects logistic regression models (for dichotomous outcomes) and mixed effects linear regression models (for continuous outcomes). Changes in these behaviors from baseline to 2, 4, 12, and 24 months will be described through odds ratios and 95% confidence intervals for logistic models, and slopes for linear models. Differences in changes over time for OHT vs. CWT will be tested through group by time interaction terms.

Aim 4: To identify subpopulations for whom the intervention has the greatest effect, we will analyze moderators; e.g., race/ethnicity, insurance coverage, parent educational level, and child's prior caries experience. This aim focuses on moderator effects (also known as effect modification) for incident caries over 24 months. We will use logistic regression models with multiplicative interaction terms (treatment group x moderator) to compare the efficacy of OHT across subpopulations.

17. Missing data: We will gather follow-up information and reasons for dropout regardless of treatment completion, censoring at the point of loss. We will examine the extent of drop-out, and identify characteristics associated with drop-out through logistic regression. Given drop-out does not exceed the expected rate of 30%, primary analyses will be based on available data. Secondary analyses will account for missing data and explore the potential impact of drop-out on study findings. We will describe the robustness of our findings with respect to missing data using inverse probability weighting. This approach to handling missing data has two steps: 1) develop propensity scores for missing data, which involves using logistic regression to model the probability of being followed to the 24 month visit as a function of baseline variables, including history of caries; and 2) using the inverse of the propensity scores (predicted probabilities from the first step) to serve as weights in our logistic regression model of new

primary teeth caries. Provided the data are missing at random (MAR), that is, the probability of missingness can be fully explained by observable data, this approach produces asymptotically unbiased estimates. If there is sufficient missing data, and a concern that data may be missing not at random, we will also consider pattern mixture models to perform a sensitivity analysis of the potential impact of missingness.

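### The covariates of the primary caries model are partly left to a p<0.10 test of between-arm differences with no candidate list, plus an undefined remainder, and site, a stratification factor, is not named

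*Combined protocol and SAP*

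**What the plan says.** Three parts of the protocol and SAP bear on the primary model.

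- **Overview of section 12.4.** "preliminary analyses will explore differences between arms and variables found to differ between groups", at the p<0.10 level, will be adjusted for. The rule covers oral health and behaviour outcomes generally. No candidates, test or test population are named.
- **Section 12.4, Primary aim 1.** Any new caries in the primary dentition over 24 months is analysed by logistic regression, "controlling for age, previous caries, and other relevant variables". The last item is not defined.
- **Sections 4 and 5.4.1.** Randomisation is "stratified by study site (Codman Square, Dorchester, BMC, South End Community Health Center), and history of caries". Caries history reaches the model as previous caries; site does not. In section 12.4, site-specific effects are mentioned only under the budget impact aim.

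The missing-data rule matters too. The overview says: "If follow-up meets the anticipated 70%, inverse probability weighting may be used in sensitivity analyses addressing the impact of missing data". The missing-data paragraph agrees: "Given drop-out does not exceed the expected rate of 30%, primary analyses will be based on available data". At or above 70% follow-up the primary analysis is therefore unweighted, and covariates are its only means of addressing imbalance among those followed.

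**The concern.** A reader cannot write down the primary model from the plan. Three things are open.

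1. **The screen.** Among all randomised dyads, any difference at p<0.10 is due to chance, so the screen selects on imbalance and not on how well a variable predicts caries. Among those followed, it may also pick up imbalance from dropout that differs by arm. The text does not say which population is meant.
2. **The unnamed remainder.** It may simply mean the screened variables, since the overview governs the Primary aim 1 text. It may also leave a choice that could be made after outcomes are seen. The wording does not settle this.
3. **Site.** Blocking balances site between arms, so a balance test will almost never select it.

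At stake is whether a result near the 0.05 boundary could depend on which reading the analyst takes.

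**Working it through.** **The plan's own figure (section 12.2).** Inputs: 300 per arm, 23.8% vs 14.3%, two-sided 0.05, unadjusted chi-square test.
- Pooled rate: (0.238 + 0.143)/2 = 0.1905. Null SE: √(2 × 0.1905 × 0.8095/300) = 0.03206.
- Alternative SE: √[(0.238 × 0.762 + 0.143 × 0.857)/300] = 0.03183.
- z = (0.095 − 1.96 × 0.03206)/0.03183 = 1.010, so power is 84.4%. The stated 84% reproduces, and it does not depend on the covariates.

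**Number of candidates (an assumption).** The baseline box of the study schematic lists 3 social cognitive measures, 12 moderators, 7 behaviours, and knowledge and attitudes (2). That is 24, or 23 without previous caries. The documents do not say that these are the screened set.

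**Chance that the screen adds something.** With k independent candidates this is 1 − 0.9^k: 41% (k = 5), 65% (k = 10), 91% (k = 23). At correlation 0.3 it is 83% for k = 23.

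**Do the two test populations select the same variables?** If 600 of 850 are followed at random, the two balance statistics have correlation √(600/850) = 0.840. For one candidate, both exceed the two-sided 0.10 limit with probability 0.0546, so exactly one does with probability 2 × (0.10 − 0.0546) = 0.091. The chance that the sets differ is 1 − (1 − 0.091)^k: 38% (k = 5), 61% (k = 10), 89% (k = 23). Simulation agrees: 39%, 59-62% and about 85-90%.

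**Effect on the verdict (simulation).** Trials randomised 850 in blocks of 2 or 4 within 8 strata and followed 600, at the planned incidences or under the null. Assumed inputs:
- site shares 40/20/20/20%
- caries history in 20% (log-odds 1.2)
- age 0.35 per SD
- 6 of 23 candidates prognostic at 0.125 per SD
- candidate correlation 0 or 0.3

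| Quantity | Result |
|---|---|
| Verdict differs between the two test populations | about 0.5-2.5% of trials |
| Type I error, screen applied mechanically | 4.4-6.1% across runs and scenarios (Monte Carlo error about 0.4-0.5 point) |
| Type I error, better of the two screens reported | 5.6-5.7%, against 4.9-5.1% for either alone |
| Type I error, any one of 23 covariates added by choice | 6.3-6.7%; 10.3% in the most extreme assumed case |
| Site selected by the screen | 0 of 20,000 (all randomised); 2 of 20,000 (followed) |
| Power gained by adding site | up to 0.2 point; 0.8 if control incidence is assumed to be 16/21/30/38% by site |

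**Dropout that differs by arm.** Assume follow-up of about 70% that depends on one prognostic variable (0.25 per SD), with log-odds +0.3 per SD in one arm and −0.3 in the other. That variable is picked in 10% of trials if all randomised are tested and in 69-70% if those followed are. The mean null log odds ratio is 0.041 with age and caries only, 0.038 screening all randomised, 0.006 screening those followed, and 0.001 when the variable is pre-specified among six fixed prognostic covariates. For scale, 0.041 is about 6% of the planned effect (ln 0.53 = −0.635; 0.041/0.635 = 0.065).

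**The case against.** The best defence is that the rule is mandatory, not discretionary. Flagged variables must enter the model, and the unnamed remainder can be read as referring to those same variables. On that reading the three openings shrink to two, and free choice largely disappears. This is a fair reading, but the text does not confirm it, and the candidate list and test population would still be missing.

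A second point also stands. Screening those followed has a real use: in the dropout scenario it removed most of the bias. Deleting the rule without a replacement would give that up, so likely dropout predictors have to be named first.

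A reader might infer that the plan inflates type I error to 6-7%. The documents do not support that as a property of the plan. A figure in that range (5.8-7.0%) arises when the best of four models is reported: age plus caries, the same plus site, and the two screened models. Once anything is flagged, the two unscreened models breach the overview's own rule. None of the four represents the unnamed remainder either. The 6.3-6.7% figure does represent it, but only if an analyst picks a covariate after seeing outcomes, which the plan does not propose.

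**Conclusion.** The gap is real and the harm is modest. The plan does not determine the primary model beyond age and previous caries, and it omits a stratification factor. The screen applied mechanically keeps type I error near 5%, the sample size is sound for its stated test, and naming site gains little power unless incidence varies widely between sites. If about 23 candidates are assumed, the two test populations usually give different covariate sets but change the verdict in only about 0.5-2.5% of trials. Choosing covariates freely after seeing outcomes could raise type I error somewhat, by an amount that rests on assumed covariate strengths. The documents give no candidate list, prognostic strengths or rates by site, so every simulated figure is conditional. The wording should be changed because the change is cheap and makes the primary model reproducible, not because the planned test is invalid.

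**What to change.** 1. In the overview of section 12.4, replace the p<0.10 rule with a fixed primary model: arm, site (4 levels), previous caries at the baseline exam, and age. The time point needs stating because section 3.2.2 measures previous caries at baseline, 12 and 24 months.
2. Under Primary aim 1, replace the open phrase with a closed list that includes baseline variables expected to predict both dropout and caries. Fix it before anyone analyses outcome data by arm and no later than database lock. A deadline tied to unblinding would not work, because section 5.4.2 leaves the PIs and Project Director unblinded.
3. For other outcomes, use arm, the stratification factors, age and the baseline value of the outcome.
4. Report baseline balance descriptively. Keep adjustment for imbalance among those followed as a named sensitivity analysis beside the planned inverse probability weighting.

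**Cost.** This is a wording change; site and baseline caries are already recorded. Site adds three parameters. With 300 × (0.238 + 0.143) = 114 expected events and six terms besides the intercept (arm 1, site 3, caries 1, age 1), that leaves 114/6 = 19 events per term before any closed-list additions. The real loss is data-driven adjustment in the primary model for dropout imbalance that nobody foresaw.

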3.2.2 Secondary

Budget impact analysis: Measures and analyses will follow best practice guidelines (Mauskopf et al., 2007). Dental public and private insurance claims will be collected from each participating site. Labor Costs: Labor time will be assessed for each dissemination scenario at each site and average salary for each personnel will be used to determine labor cost. We will measure costs of interface development, implementation, and technical support.

Pediatric oral health behaviors:

Brushing. We will assess frequency, duration, timing, and supervision of brushing using items from the BRFQ (Albino et al., 2017). This measure will be assessed at all measurement points, and during the TM program.

Bottle/sippy cup/cup use. This measure will be assessed at all measurement points, and during the TM program. We will use items from the BRFQ (Albino et al., 2017).

Diet (Food and Beverage Consumption Scale; Palmer et al., 2010; 31 food/beverage items). Participants are asked to assess their child's food intake by selecting the frequency in which each food item is consumed over the past month on a five-point Likert scale, which is scored from 0-4 and measured by the following choices: Never/Rarely; 1-2 times/week; 3-6 times/week; 1 time/day; 2 or more times/day. The food items presented are divided into 6 food categories: cereal; fruits and vegetables; grains, breads, and pastas; dairy; snacks and sweets; and drinks. Each food category contains approximately 2 or more foods or beverages. The estimated cariogenicity score is composed of 5 cariogenic categories, calculated for each child by obtaining a weighted sum of the number of food items for each food category and dividing by the total food and beverage items. This measure will be assessed at baseline, 4, 12, and 24 months after baseline.

Sugar sweetened beverage consumption (15 items). We will use the BEVQ-15 to assess sugar-sweetened beverages and total beverage energy intake (Hedrick et al., 2012). These measure will be assessed at baseline, 4, 12, and 24 months after baseline.

Tooth monitoring. We will assess the frequency of parental checking of child's teeth for early signs of cavities. This will be assessed at all measurement points. We will use items from the BRFQ (Albino et al., 2017). This measure will be assessed at baseline, 4, 12, and 24 months after baseline.

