6.2 Administration of Intervention

The TM intervention is automated and interactive. The program will begin sending TMs within 24- hours of randomization. Both OHT and CWT will be 4-months in duration, with a 1-month booster session that will occur 12 months after baseline (8 months after the end of the 4 month program). TMs will be delivered approximately twice each day in Month 1, and once per day in Months 2-4 (exclusive of brief assessment questions which occur several times per week).

During the booster session (at 12 months after baseline), TMs will be delivered approximately twice per day, exclusive of brief assessment questions. Brief assessment questions will occur several times per week. The number of texts, dose, and duration will be equivalent between the two groups. Participants in both groups will choose 'choice topics' each week, and will be assessed weekly via TM on core topics (brushing for OHT; reading for CWT) and mediators (motivation, self-efficacy and outcome expectations). Monthly assessments include dental visits (OHT) or safety (CWT)

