12 STATISTICAL CONSIDERATIONS

12.1 Study Hypotheses

Primary hypothesis 1: Those receiving OHT will have lower 24 month incidence of any new caries, compared to those receiving CWT.

Primary hypothesis 2: The OHT effect on new caries at 24 months will be mediated through Social Cognitive Theory constructs (self-efficacy, motivation, and outcome expectations). We will examine indirect effects of OHT through self-efficacy, motivation, and outcome expectations at 2 months, to potentially increased motivation and oral health behavior at 4 months (end of intervention) to new caries at 12 and 24 months. We will also examine indirect effects of OHT through self-efficacy, motivation, and outcome expectations at 4 months (end of treatment), to potentially increased motivation and oral health behavior at 12 months and to new caries at 12 and 24 months.

Secondary hypothesis 1: We hypothesize that the total cost of OHT implementation will be more cost-effective than standard of care (e.g., oral health anticipatory guidance).

Secondary hypothesis 2: Those receiving OHT will have better pediatric oral health behaviors (tooth brushing, diet, sugar-sweetened beverages, fluoride toothpaste use, preventive dental visits, and oral assessment by parents) at 4 months (end of intervention), 12 months, and 24 months, compared to those receiving CWT.

Secondary hypothesis 3: Those receiving OHT will have better oral health behaviors (tooth brushing, dental visits), oral health knowledge, and attitudes at 4 months (end of intervention), 12 months, and 24 months, compared to those receiving CWT.

Exploratory Analyses: These analyses will explore whether the effect of OHT vs. CWT on new caries at 24 months is greater in subpopulations defined by race/ethnicity, insurance coverage, parent education level, child's prior caries experience, parent depressed mood, and intervention dose/engagement.

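### Continuous outcomes under secondary Aims 2 and 3 are summarised by slopes with the coding of time unstated; a linear slope would not estimate the effects hypothesised at 4, 12 and 24 months

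*Combined protocol and SAP*

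**What the plan says.** Section 12.4 plans mixed models for the secondary behaviour outcomes: "Continuous variables (e.g., number of tooth brushings per week) will be analyzed through mixed effects linear regression models", with mixed logistic models for dichotomous outcomes. Under Aims 2 and 3 the summary measures are as follows.

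- Dichotomous outcomes: "Changes in these behaviors from baseline to 2, 4, 12, and 24 months will be described through odds ratios", with confidence intervals.
- Continuous outcomes, and the comparison of arms: "and slopes for linear models. Differences in changes over time for OHT vs. CWT will be tested through group by time interaction terms".

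The coding of time in these models is not stated.

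In section 12.1, secondary hypotheses 2 and 3 expect better results in the OHT arm "at 4 months (end of intervention), 12 months, and 24 months, compared to those receiving CWT".

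Section 6.2 sets the exposure: "Both OHT and CWT will be 4-months in duration, with a 1-month booster session that will occur 12 months after baseline". The Description of Intervention in the Protocol Summary places that booster after the 12-month assessment.

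For several of the measures concerned, including diet, parent knowledge and parent attitudes, section 3.2.2 says: "This measure will be assessed at baseline, 4, 12, and 24 months after baseline". Brushing, bottle and cup use, and preventive dental visits are also collected at 2 months.

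**The concern.** The hypotheses concern three separate times, whereas a slope is a rate of change over the whole follow-up. If time enters the model as a single linear term, no parameter corresponds to the OHT–CWT difference at month 4, 12 or 24, and the test of the interaction is a test of whether the arms drift apart at a constant rate for 24 months.

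The design gives reason to doubt a constant rate. The main programme runs for 4 months, and an 8-month gap without texts precedes the 12-month survey. The booster follows that survey and the next survey is at 24 months, so no survey falls close to the booster. An effect that is largest at month 4 is therefore plausible, although the documents do not predict one. On a linear time scale the 24-month visit has the most leverage and is furthest from the main programme.

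At stake are the conclusions on child behaviours and on parent behaviours, knowledge and attitudes. A real effect at the end of the programme could be reported as no difference, or as a decline in the treated arm. Leaving the coding open also lets it be chosen after the data have been seen.

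**Working it through.** **Plan's own figures.** The documents give no power, SD, within-person correlation or effect shape for these outcomes, so there is no stated figure on this point to reproduce. The sample of 300 per arm comes from section 12.2. The 84% stated there for caries does reproduce: with 23.8% vs 14.3%, the pooled SE is 0.03206 and the unpooled SE 0.03183, so (0.095 − 1.96 × 0.03206)/0.03183 = 1.01 and power is 0.844.

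**Assumptions.** SD 1; 300 per arm with complete data; compound symmetry with correlation ρ = 0.3 or 0.5; visits at 0, 2, 4, 12 and 24 months; two-sided alpha 0.05 (section 12.4).

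**Linear slope.** Mean visit time is 8.4 months. The deviations are −8.4, −6.4, −4.4, 3.6 and 15.6, with sum of squares 387.2. For arm differences d(t):

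- slope difference b = Σ(t − 8.4)d(t)/387.2
- SE(b) = √[2(1 − ρ)/(300 × 387.2)] = 0.00347 (ρ = 0.3) or 0.00293 (ρ = 0.5)
- power = Φ(|z| − 1.96) + Φ(−|z| − 1.96), with z = b/SE

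**Visit contrast (difference in change from baseline).** SE = √[4(1 − ρ)/300] = 0.0966 or 0.0816. A difference of 0.3 SD gives z = 3.11 or 3.67, so power is 87–96%. A difference of 0.2 SD gives 54–69%, and 0.1 SD gives 18–23%.

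**Joint group-by-visit test (4 df).** Non-centrality = 300 Σ(d − mean d)²/[2(1 − ρ)].

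| Arm difference (SD) at 0, 2, 4, 12, 24 months | Σ(t − 8.4)d | b × 24 | Slope power | Month-4 contrast | Month-12 contrast | Month-24 contrast | Joint test |
|---|---|---|---|---|---|---|---|
| Partial fade: 0, 0.2, 0.3, 0.2, 0.1 | −0.32 | −0.02 | about 6% | 87–96% | 54–69% | 18–23% | 77–90% |
| Sustained: 0, 0.2, 0.3, 0.3, 0.3 | 3.16 | 0.20 | 65–79% | 87–96% | 87–96% | 87–96% | 88–97% |
| Growing: 0, 0.1, 0.2, 0.3, 0.3 | 4.24 | 0.26 | 88–96% | 54–69% | 87–96% | 87–96% | 88–97% |
| Fade to zero: 0, 0.2, 0.3, 0.15, 0 | −2.06 | −0.13 | 33–44% (negative slope) | 87–96% | 34–45% | no effect | 88–97% |

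For the partial fade, for example, −6.4 × 0.2 − 4.4 × 0.3 + 3.6 × 0.2 + 15.6 × 0.1 = −0.32. Dividing by 387.2 gives −0.00083 SD per month, or −0.02 SD over 24 months.

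**What the line estimates in that case.** The mean difference is 0.16, so the fitted intercept is 0.16 + 0.00083 × 8.4 = 0.167 SD. The model then puts the arm difference at 0.17, 0.16, 0.16 and 0.15 SD at months 0, 4, 12 and 24, where the assumed truth is 0, 0.3, 0.2 and 0.1. The early effect has moved into the group main effect, which the plan does not test.

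**Measures without a 2-month visit.** With visits at 0, 4, 12 and 24 months and differences of 0, 0.3, 0.2 and 0.1 SD, the slope difference is exactly zero: the mean time is 10, and −6 × 0.3 + 2 × 0.2 + 14 × 0.1 = 0. Its power is then the 5% test size.

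**The case against.** A reader might infer that the plan fits one straight line over 24 months to every secondary behaviour outcome and so will miss the intervention's effect. The documents do not support that.

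- **Coding of time.** It is unstated. The same sentence lists changes from baseline to each visit, and it speaks of slopes and terms in the plural, which fits a categorical visit factor. With that coding, the group-by-visit terms would test the hypotheses. This stands: the defect is an unspecified coding together with a word that points to linear time.
- **Scope.** Only continuous outcomes get slopes. Dichotomous outcomes already get odds ratios, and share the problem only if time is linear in their interaction.
- **Shape of the effect.** The fade is an assumption. The hypotheses name benefit at all three times, which is closer to a sustained effect, and there is a booster at month 12. If the effect grows, the slope does about as well as the joint test and better than the month-4 contrast.
- **Limits of the remedy.** Under the partial fade, the month-24 contrast has only 18–23% power, so visit contrasts would usually miss that effect too.
- **Mechanism.** A reader might also infer that a null slope would lead the trial to conclude that the mechanism failed. Mechanism is tested separately under Primary Aim 2, with mediators and behaviour taken at named visits.
- **The 2-month change.** This is a minor point. The visit is right for brushing, bottle and cup use, and dental visits, and wrong only for measures not collected then.

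These points narrow the concern without removing it. A plan that can be read either way does not fix the estimate for hypotheses 2 and 3.

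**Conclusion.** The concern holds for the continuous outcomes of secondary Aims 2 and 3, as a mismatch between visit-specific hypotheses and a slope summary with time coding left open. On the linear reading, the planned summary does not estimate the hypothesised effects whatever their shape.

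The loss of power depends on a shape that the documents do not give. Under the stated assumptions, slope power runs from about 6% (partial fade) through 65–79% (sustained) to 88–96% (growing). A fade to zero produces a negative slope that is significant in 33–44% of trials although the treated arm was never worse. The correlation range and complete data are also assumptions; section 12.2 expects 70% of dyads to be examined at 24 months, and 300 per arm is that analysis sample.

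The point should be corrected before analysis but is confined to secondary outcomes. The primary caries analysis, its 84% power and the mediation analysis are untouched.

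**What to change.** Amend section 12.4, Aims 2 and 3, as follows.

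1. State that visit is a categorical factor in the mixed models, for binary outcomes as well as continuous ones.
2. For each measure, use only the visits at which it is collected. Drop the 2-month change for diet, sugar-sweetened beverages, fluoride, knowledge and attitudes. Section 3.2.2 gives two different schedules for tooth monitoring; reconcile these first.
3. Name the OHT–CWT differences in change from baseline at 4, 12 and 24 months as the estimates for secondary hypotheses 2 and 3, with odds ratios for binary outcomes.
4. Delete the reference to slopes, or label them descriptive.

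The cost is analysis-plan wording and a few more degrees of freedom: the interaction has 4 with five visits, or 3 with four, instead of 1. A single-visit contrast also has less power than a slope if the effect grows steadily, as with the month-4 contrast in the growing profile (54–69% against 88–96%). No new data, visits or participants are needed.
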